### B1. PURPOSE OF PROTOCOL

Nitrous oxide is a well-tolerated inhaled sedative that has been used for decades in pediatric and adult populations and is largely viewed as effective and safe. In addition to analgesic effect, nitrous oxide also produces a dissociative euphoria and amnesia that could potentially improve patients' anxiety and experience of cancer care. Over the past several decades nitrous oxide has become less common due to concerns of nitrous oxide environmental exposure to the care team. There are now FDA-approved systems that allow patient self-administered nitrous oxide (SANO), and importantly, include a scavenger system to eliminate exhaled environmental nitrous oxide. These systems are rapidly being adopted throughout the US in Urology practices, but to date, there have been no studies evaluating patient outcomes and possible risks with the adjunct use of SANO. We propose a prospective, randomized, controlled trial to assess patient perceived pain and anxiety related to prostate needle biopsy with or without SANO, and the frequency of complications associated with SANO. A secondary aim will be to demonstrate that the SANO at the time of prostate biopsy does not significantly increase burden on Urologist productivity, nor increase the difficulty of operator ease in performing the prostate needle biopsy.

#### Specific Aims:

**Aim 1:** To determine the effectiveness of Self-Administered Nitrous Oxide (SANO) in decreasing patient perceived anxiety and pain related to prostate needle biopsy.

*Hypothesis 1.1: Patients receiving periprocedural SANO will have decreased anxiety during the procedure, as measured by STAI (State-Trait Anxiety Inventory) score, situational pain catastrophizing scale (SPCS) and patient vital signs.*

*Hypothesis 1.2: Patients receiving periprocedural SANO may have a decrease in pain as measured by VAS (visual analogue scale) score and patient vital signs.*

**Aim 2:** To demonstrate that the SANO at the time of prostate biopsy does not significantly increase burden on Urologist productivity, nor increase the difficulty of performing the biopsy.

*Hypothesis 1.1: Administration of periprocedural SANO will not significantly lengthen the time of the procedure relative to local anesthetic alone.*

*Hypothesis 1.2: Administration of periprocedural SANO will result in minimal side effects for the patients and will allow the patient to drive home independently.*

*Hypothesis 1.3: Administration of periprocedural SANO will allow the operating Urologist to perform the procedure with the same ease as on those patients who do not have SANO.*

## B2. SIGNIFICANCE AND BACKGROUND FOR THE STUDY

### Burden of Transrectal Prostate Biopsies in the US

The number of prostate biopsies performed on US men annually is nearing 2 million (Wolinsky, 2021). Transrectal prostate needle biopsy is a very common procedure in the US that is associated with significant anxiety and discomfort for men. Historically, a prostate needle biopsy is performed via a transrectal ultrasound probe with a lidocaine local anesthetic block, without sedation or general anesthesia. In part, the prostate biopsy is performed without sedation or anesthesia due to added cost and time associated with an anesthesia team required for most anesthesia agents.

Until the early 2000s, prostate biopsy was frequently performed without the aid of local anesthetic. Current practice is to perform prostate biopsies with a periprostatic block using 10 ml of 1% lidocaine. Even with an anesthetic on board, studies have demonstrated the significant psychological impact of prostate needle biopsies, and this is further compounded in those patients requiring repeat biopsy.

Factors influencing the development of pain during a prostate biopsy can be divided into patient-associated factors (younger age, smaller prostate, and pre-biopsy anxiety) and procedure-associated factors (number of cores, use of local lidocaine block). With the advent of MRI fusion technology, we can now target suspicious areas with greater accuracy. However, this comes with the additional probe manipulation within the rectum and additional biopsies of suspicious areas, which has been associated with greater patient pain and anxiety (Chesnut, 2020).

### Nitrous Oxide as an adjunct for Procedural Pain

Nitrous oxide has been used in dental offices for decades, accepted for both its analgesic and anxiolytic properties. The exact mechanism of action is not clear, but recent studies have hypothesized that the analgesic effect is from release of opioid peptides and stimulation of opioid receptors. The anxiolytic properties of nitrous oxide have been compared to benzodiazepine GABA-ergic pathway, resulting in moderate sedation, thereby reducing anxiety. Administration can be controlled by the patient and the effect of nitrous oxide is realized within 2-3 minutes with elimination within 2-3 minutes. Nitrous oxide can be administered either independently or as an adjunct to locoregional blocks. These properties of nitrous oxide have led to becoming a standard of care in Obstetrics and Gynecology (AWHONN Practice Brief, 2018). In the United States, spinal analgesia is more commonly used than nitrous oxide during childbirth; however, nitrous oxide is routinely used elsewhere, with reported rates of 73% in Canada and 62% in the United Kingdoms. In Europe, Entonox, a 50% nitrous oxide: 50% oxygen mixture, is widely used in emergency medical care of patients in accident scenes and for mild sedation and analgesia.

#### **Administration:**

Inhaled nitrous oxide is typically administered at 30-70% concentration, mixed with oxygen. In dental practice, a nasal hood connected to a flometer is used to deliver the nitrous oxide. Typically, a separate tube associated with the nasal hood is connected to wall suction to scavenge the

exhaled waste gas. One of the key reasons nitrous has fallen out of favor in some settings is because the scavenging through a nasal hood is ineffective at containing and eliminating all exhaled nitrous.

The Nitrouseal® system has an adjustable-concentration digital flowmeter and includes an FDA-cleared exhaled waste gas scavenger, the Miniscav®. The Nitrouseal® system includes a proprietary disposable single-use full-face mask and breathing circuit that collects and contains the exhaled nitrous gas before it is scavenged into the Miniscav®.

It has been used in urology since 2017 in procedures such vasectomies, cystoscopies, UroLift® implants, bladder biopsies, prostate biopsies and Botox injections, with reported improvement in patient anxiety, relaxation and comfort. However, there have been no randomized controlled studies in the US that have studied the effects of nitrous oxide for prostate biopsies thus far.

### B3. DESCRIPTION OF RESEARCH PROTOCOL

#### A. Study Design – Overview, Methods, Procedures

##### METHODS AND PROCEDURES:

###### **Screening**

After the Urologist has discussed and planned for prostate needle biopsy, the study team will examine the list of scheduled biopsies for the week, and a baseline examination by the clinical team for eligibility verification will be performed through a medical record review by a trained member of the research staff.

###### **Recruitment and Obtainment of Informed Consent**

A member of the research team will reach out by phone call and/or PatientSite email at least 1 week before their scheduled biopsy. When discussing prostate biopsy with the attending urologist, study will be introduced to patient and provide a flyer on laymen terms describing the protocol, risks and benefits and information about enrollment. When discussing prostate biopsy with the attending urologist, study will be introduced to patient and provide a flyer on laymen terms describing the protocol, risks and benefits and information about enrollment. The phone call (or PatientSite message) will give a brief description of the research study. If the patient expresses interest in learning more about the study during the phone call (or by replying to the PatientSite message), a member of the study staff will then send a secure email to the patient with a copy of the informed consent form. Following this, a member of the study staff will call the patient to review the consent form and answer questions. Special care will be taken during the consent process to ensure subjects are fully competent and understand the nature of the questionnaires, as well as the nature of the randomization process (that they may receive Oxygen rather than SANO). If the patient desires to participate in the study, they will be asked to sign the electronic consent form on REDCap (Electronic Informed Consent (eIC)). Study staff will then send subjects an email containing a PDF version of the eConsent signed by both the subject and the staff member obtaining the consent.

Efforts will be made to attain a mix of study participants in terms of racial/ethnic representation, which is reflective of the population of the greater metropolitan Boston area: 63% white, 26% African American and 11% other.

###### **Baseline Assessment:**

After informed consent has been obtained, the patient will be directed to a REDCap questionnaire that will collect demographics, general medical history, and prior prostate biopsy information (See Pre-Procedure Evaluation Survey). This will be reviewed by research personnel to confirm eligibility to participate in the study based on pre-determined inclusion and exclusion criteria. If they do not qualify for the study, they will not be randomized to either arm, and will undergo a standard template biopsy with local anesthesia only.

In addition, patients will complete the Brief Pain Inventory, a well-validated measure that assesses intensity of current pain and interference of pain in the patient's life (Dworkin, 2005). If the patient

does not complete these two questionnaires electronically before the day of procedure, they will be offered the opportunity to complete on the day of their procedure prior to the biopsy.

### **Randomization**

Subjects will be randomized 1:1 to either SANO (treatment) or oxygen (placebo control) after completion of baseline assessment. The results of the randomization will not be disclosed to patients as part of the study (patient-blinded). The randomization module in REDCap will be used to implement randomization of the subject to our two study groups.

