## C. Subject Selection

### Subject Population

The study population will be all patients aged 21 to 85 years referred for prostate needle biopsy (both standard sextant and MRI-fusion guided) to BIDMC within 6 months' period. A total of 152 patients will be enrolled for the study.

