### Eligibility Criteria

#### *Inclusion criteria:*

- (1) Biological male
- (2) Aged 21 to 85 years
- (3) Scheduled for prostate needle biopsy
- (4) No learning disabilities
- (5) Suitable for nitrous oxide/oxygen IHS with willingness to be randomized to inhaled SANO or inhaled oxygen during the procedure
- (6) Access to an email and computer

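### Biopsy type and prior biopsy, which the protocol itself ties to the trial's outcomes, enter neither the allocation nor the analysis, so some precision is given up

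*Combined protocol and SAP*

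**What the plan says.** Subject Population takes men "referred for prostate needle biopsy (both standard sextant and MRI-fusion guided) to BIDMC". The relevant inclusion criterion is only "Scheduled for prostate needle biopsy", with no restriction to first biopsies. Baseline Assessment collects prior-biopsy history, and Data Analysis gives men with a prior biopsy an extra 13-item catastrophizing questionnaire, so repeat biopsies are plainly expected.

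Section B2 (Burden of Transrectal Prostate Biopsies in the US) says that MRI fusion brings "additional probe manipulation within the rectum and additional biopsies of suspicious areas, which has been associated with greater patient pain and anxiety". Of the psychological impact of biopsy it says that "this is further compounded in those patients requiring repeat biopsy".

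On allocation, the Randomization section says "Subjects will be randomized 1:1 to either SANO (treatment) or oxygen (placebo control) after completion of baseline assessment" and "The randomization module in REDCap will be used to implement randomization of the subject to our two study groups". It mentions no strata, blocks or minimisation. Data Analysis names VAS and VAS-A as the primary measures and expresses interest in the between-arm difference. It gives no test, model or covariate. Biopsy type does not appear there, and prior biopsy appears only as the trigger for the 13-item questionnaire.

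**The concern.** The protocol itself identifies two features of the biopsy as related to what the trial measures: fusion guidance (pain and anxiety) and repeat biopsy (psychological impact). Prior biopsy is known before randomisation, because randomisation follows the baseline questionnaire. Planned biopsy type should be known too, since screening works from the list of scheduled biopsies, although the protocol does not say that the list records the type.

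If neither factor is used, a chance imbalance between the arms moves the observed difference, and the variation that the factors explain stays in the error term. The stake is precision in a trial planned at 80% power with no reserve beyond the dropout allowance. A second stake is that, without a prespecified choice, any adjustment made after an imbalance is seen would be post hoc.

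**Working it through.** **The plan's own figure.** Sample Size Justification gives an STAI SD of 8, a difference of 4 points (4/8 = 0.5 SD), alpha 0.05 and power 80%.
- Normal approximation, two-sided: n = 2 × (1.96 + 0.84)² × (8/4)² ≈ 63 per arm.
- Two-sample t-test: 63.8, so 64 per arm. The stated 64 reproduces.
- Dropout: 64/0.85 = 75.3, so 76 per arm and 152 in total. This also reproduces.

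**Inputs the documents do not give (assumed).** The share of men with a given factor is taken as 30-50%. The effect of a factor on the outcome is taken as 0.5 SD, with a range of 0.3-0.7 SD and a check at 0.2 SD.

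**Chance of imbalance.** This is the probability that the two arms' proportions differ by at least 10 percentage points on one factor, computed in two ways:

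| Method | Per arm | 30% have factor | 50% have factor |
|---|---|---|---|
| Independent binomial arms | 76 | 18.4% | 22.4% |
| Independent binomial arms | 64 | 21.0% | 25.0% |
| Fixed equal arms (hypergeometric) | 76 | 21.6% | 25.6% |
| Fixed equal arms (hypergeometric) | 64 | 17.5% | 21.6% |

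The methods differ because counts are discrete. Either way the answer is about one in five to one in four per factor.

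**What such an imbalance does.** Shift = imbalance × factor effect.
- At 0.5 SD: 0.10 × 0.5 = 0.05 SD. On STAI that is 0.05 × 8 = 0.4 points, a tenth of the 4-point target.
- Range: 0.10 × 0.3 = 0.03 SD to 0.10 × 0.7 = 0.07 SD.
- Standard error of the difference at 64 per arm: √(2/64) = 0.177 SD. So 0.05/0.177 = 0.28 of one standard error.

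**Gain from adjusting for one factor.** For a 50:50 factor with effect d (in SD), R² = 0.25 × d². The standardised target becomes 0.5/√(1 − R²). Two-sample t-test power at 64 per arm:

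| d (SD) | R² | Power |
|---|---|---|
| no adjustment | 0 | 80.1% |
| 0.2 | 0.0100 | 80.5% |
| 0.3 | 0.0225 | 81.0% |
| 0.5 | 0.0625 | 82.6% |
| 0.7 | 0.1225 | 85.0% |

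No increase in sample size is involved.

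**The case against.** The strongest reply is that nothing here is invalid. Unstratified 1:1 randomisation gives an unbiased comparison, and the ordinary standard error already allows for chance imbalance in factors left out of the model. That stands. A reader might infer that an imbalance biases the result; it does not. The 0.05 SD is random error in the realised estimate, and it is small beside a standard error of 0.177 SD.

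Further points also stand:
- **Repeat biopsy and pain.** A reader might infer that the protocol ties both factors to both outcomes. It names pain and anxiety for fusion, but only psychological impact for repeat biopsy. A power gain computed for two equal, independent factors acting on the same outcome therefore has no basis in the documents for pain, and none is claimed here.
- **Scale.** The 0.5 SD target comes from STAI. No SD or target difference is given for VAS or VAS-A, so the power figures cannot be read as applying to those measures.
- **Choice of covariates.** Section B2 also lists anxiety before biopsy among the factors behind pain. Pre-procedure Evaluation collects STAI and VAS from every patient, and these baseline scores may well be the stronger covariates. They belong in the model beside the two biopsy factors.
- **Silence is not exclusion.** The protocol does not say that allocation is unstratified or that scores will be compared raw; it specifies neither strata nor model. Strata may exist in REDCap, in which case they need only be stated and carried into the analysis.
- **Strata add little to the quantified gain.** The power figures come from the covariates. Stratifying only limits imbalance.

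The reply does not remove the point itself. The protocol calls these features relevant, one is already collected, and using both costs almost nothing. The 13-item questionnaire cannot stand in for prior biopsy, because only men with a prior biopsy complete it.

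**Conclusion.** The concern holds as a matter of precision and prespecification, not of validity. The trial mixes biopsy types and biopsy histories that section B2 links to its outcomes, and no stated part of the allocation or analysis uses either factor.

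The cost is modest: about a one-in-five to one-in-four chance per factor of an imbalance of 10 percentage points or more, worth about 0.05 SD, and a forgone power gain of roughly 1 to 5 percentage points for one factor. These sizes rest on an assumed prevalence of 30-50% for the imbalance and 50% for the power gain, an assumed effect of 0.3-0.7 SD, and the STAI-based target. At 0.2 SD the gain is under one point. The change should be made because it is cheap, not because the trial would fail without it.

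**What to change.** In Data Analysis, prespecify a model for the anxiety and pain comparisons (STAI, VAS, VAS-A and S-PCS) with treatment arm, planned biopsy type (standard or MRI-fusion), prior biopsy (yes or no) and the pre-procedure score of the same measure where it is collected. Pre-procedure Evaluation lists STAI and VAS, whereas the Privacy section lists VAS, VAS-A and S-PCS before and after the procedure. The plan should settle which baseline scores exist.

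If enrolment has not started, also stratify the REDCap randomisation by the two factors: 2 × 2 = four strata with permuted blocks, workable for 152 men. If enrolment has started, leave the allocation unchanged and add only the covariates, fixing them before any unblinded analysis. If strata already exist in REDCap, state them.

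The cost is a sentence or two in the analysis text and, where still possible, a new allocation table in a module already in use. No extra patients are needed. The small downside is that planned biopsy type must be recorded at randomisation and may occasionally change on the day; the analysis should use the planned type.

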### **Pre-procedure Evaluation**

On the day of the biopsy, current standard procedure is to bring the patient to an exam room (separate from the biopsy room) where pre-procedure vitals are obtained. At this time, the pre-procedure STAI and VAS scores will be obtained. Information of inhaled gas administration and how to self-administer will be explained to the patient using templated verbal instructions. It will be emphasized that if at any point during the procedure, the patient feels uncomfortable with the inhaled gas, the team will help remove the mask.

### **Periprocedural Intervention**

The patient will be moved to the biopsy room and standard procedure for lateral positioning and explaining prostate biopsy will be done in the routine manner preferred by the individual Urologist. Oxygen saturation monitor will be applied to the patient's finger and monitored throughout the procedure. The patient's heart rate will also be monitored accordingly.

The inhalation gas mask will be positioned on the patient's face, and the patient will then be instructed to begin breathing as previously instructed. Initially the patient will receive 100% oxygen at 10 Liters/minute. In the control group, this will be continued throughout the procedure.

After the Urologist describes the procedure, the SANO group will have nitrous oxide turned on to 30%, ensuring that the patient is relaxed but still conversant through the procedure. The nitrous will be adjust up or down based on the patient's response to the question "are you feeling the nitrous" and "are you happy at this level". The range will be between 25 - 45%. This may take 2-3 minutes. Both groups will be asked these questions. Both groups will be asked to take several deep breaths before inserting the rectal probe. The prostate biopsy for both study and control participants will include the normal routine administration of local peri-prostatic nerve block using preferred technique of the individual Urologist. During the procedure, the patient and patient's oxygen saturation will be monitored by a [name], APP, or MD (separate from MD performing the procedure) and if at any point in time the patient is unhappy with gas inhalation, the observer will aid the patient in removing the mask. At the end of the procedure, the SANO group will be turned down to 0% nitrous oxide, and 100% oxygen will be administered through the mask for an additional 2-3 minutes as the patient is cleaned up and repositioned to the supine position. Assessment of the "time in" and "time out" of the procedure room will be recorded.

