### Data Analysis

All data will be collected and stored securely using the REDCap system. Data will be managed and analyzed by the PI and biostatistical support team at the BIDMC FIRST program. A Data Transfer Agreement will be created to allow for the study team's statistician, [name] MD/PhD at Brigham and Women's Hospital, to obtain and perform statistical analysis on de-identified data. At the conclusion of the study, de-identified study data will be exported out of REDCap and sent to [name] in a secure file via email message. Data will not be transferred until this agreement is approved and fully executed by both parties.

Primary outcome measure is patient anxiety and pain levels in the N2O group vs the oxygen only group as measured by the VAS and VAS A scores. We are specifically interested in the difference in scores between the two groups. Prostate biopsy mean VAS score with local anesthetic is around 3-4. We will also obtain a baseline pain index between the two groups. We will compare the perioperative VAS and VAS-A scores to the retrospective VAS and VAS-A scores collected during the survey administered 2-10 months after their biopsy.

We will also be obtaining 6 question Situational Pain Catastrophizing Scores for both groups and will compare the variation in response. Patients who have had a prior biopsy will also fill out a 13 question Pain catastrophizing score, which we will use as a baseline measure for biopsy related anxiety and hesitation.

Additional metric will include duration of biopsy, as measured by time in/time out of the procedure room for patients administered either nitrous or control oxygen when compared to patients who do not consent to the study (and will have no gas applied). Operator ease in performing the biopsy will be measured by 3 simple questions assessing patient positioning and ease of transrectal probe insertion. Prostate biopsies are generally performed as an outpatient procedure and patients can drive themselves home in most situations. Post biopsy side effects and ability of the patient to drive themselves home will be used as a surrogate to determine practicality of administering SANO in the outpatient setting.

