## **B7. STUDY LOCATION**

### **Privacy**

The study will be conducted on the premises of BIDMC Longwood Campus. We will obtain lists of patients intended for prostate biopsies in the following week, and study team members will review the OMR records for inclusion and exclusion criteria. The patient will be contacted by phone either from in-office phone call or through Doximity phone application (which provides the BIDMC Urology office as the caller ID). We will ask the patient whether they are in a location that affords privacy for discussion of medical information. If they are not, we will arrange an appropriate time when the patient will have privacy for study discussion. Phone interviews by study team members will be conducted in private space to avoid the interview being overheard.

Pre-procedure questionnaires will be emailed to private patient email via the REDCap server. Data collected will be kept within the REDCap server. Access to our REDCap will only be allowed for study team members who are trained in protecting PHI.

Operator Surveys will be on paper forms with patient identifying sticker on the form. At the end of the biopsy, the data will be input into the REDCap system by a study team member, and the paper version will be disposed of in a disposal unit intended for medical information waste.

Pre-procedure and post-procedure VAS, VAS-A score and Situational Pain Catastrophizing Score (S-PCS) and Trails-making Part B tests will be obtained in a private exam room where only the patient, study team members, and clinical staff measuring vitals will be present. Questionnaire answers will be input by the patient into a tablet computer. The tablet computer will be wiped with sanitizing wipe between uses given current COVID pandemic.

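### The titration exchange gives SANO patients a response that is not written for oxygen patients, an avoidable cue to the arm in a patient-blinded trial with self-reported primary outcomes

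*Combined protocol and SAP*

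**What the plan says.** The Randomization section sets out the blind: "The results of the randomization will not be disclosed to patients as part of the study (patient-blinded"). No blinding of staff is described. Under Recruitment and Obtainment of Informed Consent, patients are told that they may be given oxygen instead of SANO, so each patient knows that there are two possibilities.

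The Periprocedural Intervention section starts everyone on 100% oxygen at 10 L/min. For controls, "In the control group, this will be continued throughout the procedure". SANO patients are switched to 30% nitrous oxide, which is then moved within 25-45% according to the answers to two scripted questions. One is "are you feeling the nitrous"; the other asks whether the patient is happy at the current level. The section adds: "Both groups will be asked these questions". It describes no action after an oxygen patient's answer.

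For the end of the biopsy the section says: "At the end of the procedure, the SANO group will be turned down to 0% nitrous oxide". A further 2-3 minutes of mask oxygen follows. Nothing is written about the control arm's mask at that point.

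The Data Analysis section names VAS (pain) and VAS-A (anxiety) as the primary outcome measures. On their collection, the Privacy section says: "Pre-procedure and post-procedure VAS, VAS-A score and Situational Pain Catastrophizing Score (S-PCS) and Trails-making Part B tests will be obtained in a private exam room". The Periprocedural Data Collection section places STAI and S-PCS in the recovery room after the biopsy. No section records which gas the patient believes he received.

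**The concern.** Pain and anxiety scores depend on what the patient expects and believes, and the patient blind is the only blind that the protocol declares. Putting the same questions to both arms looks like a masking step, but it masks fully only if what follows the answer also looks and sounds the same. As written, a SANO patient who says he feels nothing can have his gas adjusted and, presumably, be asked again. An oxygen patient who gives the same answer has no scripted follow-up. The question has directed his attention to whether a drug is acting, and the absence of a response may help him conclude that none is.

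At stake is whether a difference in VAS or VAS-A can be read as a drug effect. If belief about the arm differs between groups and belief shifts the scores, part of the difference reflects expectation. The VAS and VAS-A are also asked again at 2-10 months, so a belief formed in the procedure room could carry into that comparison. Nitrous oxide will unblind some patients through its own effects. That part cannot be removed; the part due to the script can.

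**Working it through.** **1. The two arms side by side (Periprocedural Intervention)**

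| Step | SANO | Oxygen |
|---|---|---|
| Questions asked | Both | Both, same wording |
| Action after the answer | Nitrous oxide may be moved within 25-45% | None written; gas unchanged |
| End of procedure | Nitrous oxide to 0%, then 2-3 minutes more of mask oxygen | Not stated |
| Record of perceived arm | None | None |

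The first row carries no information about the arm. The second row does, to the extent that the patient notices it. The third is a gap in description: the wash-out gas is the 100% oxygen that controls already breathe, so the arms look different only if control masks come off sooner, which the text does not say.

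**2. The plan's own figure (Sample Size Justification)**

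Inputs: SD 8 (STAI), difference 4 points (0.5 SD), alpha 0.05, power 80%. A two-sided two-sample t-test needs 63.8, so 64 per group, as stated. Inflation: 64 / (1 − 0.15) = 75.3, so 76, as stated. This figure does not depend on the blinding question; it supplies the SD and the number per arm used below.

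**3. Illustration of a spurious shift**

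The documents give no figure for any expectation effect, so both inputs are assumptions:

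- Belief gap: how much more likely SANO patients are than controls to believe that they had nitrous oxide. Take 40 percentage points, range 20-60.
- Expectation effect: how far that belief lowers STAI. Take 2 points, range 1-3.

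Spurious difference = belief gap × expectation effect:

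- low: 0.20 × 1 = 0.2 points (0.2 / 4 = 5% of the 4-point target)
- middle: 0.40 × 2 = 0.8 points (20%)
- high: 0.60 × 3 = 1.8 points (45%)

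Standard error of the difference = 8 × √(2/64) = 1.414. With no true drug effect and a shift b, the two-sided rejection probability is approximately Φ(b/1.414 − 1.96) + Φ(−b/1.414 − 1.96):

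| Shift b | b / 1.414 | Normal approximation | t-test |
|---|---|---|---|
| 0 | 0 | 5.0% | 5.0% |
| 0.2 | 0.141 | 5.2% | 5.2% |
| 0.8 | 0.566 | 8.7% | 8.7% |
| 1.8 | 1.273 | 24.7% | 24.4% |

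**4. Limits of the illustration**

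The scale is STAI, because it is the only one with an SD in the documents; VAS and VAS-A are the named primary measures. The direction (favouring SANO) is assumed. The belief gap also does not separate the script from the drug. If the script alone added only 10 points, the shift would be 0.10 × 2 = 0.2, and the false-positive rate 5.2%, hardly above nominal.

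**The case against.** The strongest reply is that identical words put to both arms cannot disclose the arm. That stands. A reader might infer that asking an oxygen patient about nitrous oxide tells him that he is a control. The text does not support this: the question could equally suggest to him that he is receiving it, raise expectation in controls, and push any bias towards no difference.

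A reader might also infer that a control patient plainly sees nothing happen. The documents do not say whether a patient lying on his side with a mask on can see the flowmeter. The section on measuring gas flow describes flow adjustment without limiting it to one arm, and a SANO patient content at 30% may also get no adjustment. All of this weakens the cue. It does not remove it, because flow is adjusted to ventilation and bag filling, not to the patient's answer, so it is not a matched response to the question.

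Two other stronger readings fail. The SANO wash-out is not a demonstrated cue, for the reason given with the table; in addition, each patient experiences only one sequence and has no other to compare it with. Nor does the exchange come immediately before scoring. The questions belong to the titration described before probe insertion, so the nerve block, the biopsy and the clean-up come between them and the post-procedure scores.

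Finally, nitrous oxide partly unblinds by itself; the protocol describes euphoria and an effect within 2-3 minutes. That is true, and it limits what any change of script can achieve. It is no reason to keep an extra cue that can be taken out.

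**Conclusion.** The point holds as a risk of functional unblinding that can be reduced. A question that directs patients to look for a drug effect is followed by a possible response in one arm and by no written response in the other. The documents do not show that the script reveals the arm, and neither the size nor the direction of any bias can be derived from them. The range of about 5% to 24% for the false-positive rate rests on an assumed belief gap, an assumed expectation effect, an assumed direction and the STAI SD. Its lower end is practically no effect, and much of any belief gap would come from the drug. It shows why the matter is worth attention; it is not an estimate for VAS or VAS-A. The change is worth making because the primary outcomes are subjective, the patient blind is the only one declared, and the cost is very small. The point does not invalidate the design.

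**What to change.** In the Periprocedural Intervention section:

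1. Replace *the nitrous* with *the gas* in the scripted question, for both arms.
2. Have the monitor already present make the same visible adjustment and give the same verbal response in the oxygen arm, without changing the gas delivered.
3. State what the control arm's mask period at the end of the procedure is, so that the section shows whether the two arms look the same to the patient.

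Optionally, add one item to the post-procedure tablet survey, after the outcome scales, asking which gas the patient thinks he received. Report it by arm and treat it as descriptive: a patient who felt comfortable is more likely to guess nitrous oxide, so the item cannot separate script, drug effect and perceived benefit.

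The cost is a change of script wording, a few seconds per patient and, if adopted, one extra question. No added staff or sample size is needed. Blinding will remain imperfect because of the drug's own effects.
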